10.11 Statistical Methods and Determination of Sample Size

10.11.1 Statistical and Analytical Plan

A statistical analysis plan (SAP) will be written by Simbec-Orion and agreed by Artax Biopharma Inc prior to the locking of the database and subsequent reporting of the study data.

10.11.2 Study Variables/Endpoints

Part A (SAD):

The following plasma PK endpoints will be derived: C_{max} , T_{max} , λz , $t_{1/2}$, AUC_{0-24} , AUC_{0-t} , AUC_{0-inf} , $AUC_{\%extrapolated}$, CL/F , Vz/F .

Part B (Food Effect):

The following plasma PK endpoints will be derived: C_{max} , T_{max} , T_{lag} , λz , $t_{1/2}$, AUC_{0-24} , AUC_{0-t} , AUC_{0-inf} , $AUC_{\%extrapolated}$, CL/F , Vz/F .

Part C (MAD):

The following plasma PK endpoints will be derived on Day 1: C_{max} , T_{max} and AUC_{0-24} , (AUC_{0-t} will also be derived if dosing interval other than q.d).

The following plasma PK endpoints will be derived on Final Dosing Day : C_{max} , T_{max} , λz , $t_{1/2}$, AUC_{0-24} , ($AUC_{0-\tau}$ will also be derived if dosing interval other than q.d.), AUC_{0-t} , AUC_{0-inf} , $AUC_{\text{extrapolated}}$, CL/F and Vz/F .

The following urine PK parameters will be derived on Day 1 and Final Dosing Day: Ae , $Ae\%$, CL_R .

Safety endpoints:

- AEs.
- Laboratory safety (biochemistry, haematology, coagulation, and urinalysis).
- Vital signs (systolic/diastolic blood pressure, heart rate, oral body temperature and respiratory rate).
- 12-lead ECG (Heart rate, PR interval, QRS width, RR interval, QT interval and QT interval corrected using Fredericia's formula (QTcF)).

10.11.3 Analysis Sets

Safety Set: All randomised participants who receive at least 1 dose of IMP will be included in the safety analysis.

PK Set: The PK set will include participants who receive IMP (one dose in Part A, both doses in Part B (fed/faasted), up to 10 doses in Part C), have sufficient plasma concentration-time profiles and comply with the following criteria:

- Do not have an occurrence of vomiting (that occurs at or before 2 times median T_{max} within the appropriate cohort or treatment) or diarrhoea which renders the concentration profile unreliable; For Part C this applies to PK sampling days only
- Do not use a concomitant medication which renders the concentration profile unreliable;
- Do not have a Day 1 pre-dose concentration that is greater than 5% of the corresponding C_{max} ;
- Have at least one pharmacokinetic sample with concentration above the lower limit of quantitation (LLOQ);
- Do not violate the protocol in such a way that may invalidate or bias the results (major protocol violators).

10.11.4 Description of Statistical Methods

All statistical analysis will be performed using SAS[®] (the most up to date version will be used and this will be documented in the SAP).

10.11.5 Demographic and Background Data

All demographic and background data will be listed, in addition:

Disposition: Participant disposition will be listed with any withdrawals flagged. Frequencies (number and %) of the total number of participants dosed, completed, and prematurely

discontinued (including reason for discontinuation) from the study will be summarised. Additionally, the frequency of participants within each analysis set will be summarised.

Demographics: Demographic data will be listed. Descriptive statistics (number of participants in the analysis set (N), number of participants with non-missing observations (n), mean, standard deviation (SD), minimum, median, and maximum) will be tabulated for the continuous variables age, height, weight and BMI and frequencies (number and %) for the categorical variable race.

10.11.6 Efficacy Data

Not applicable.

10.11.7 Safety Data

All safety data will be listed, in addition:

AEs: All AEs will be coded using the Medical Dictionary for Regulatory Activities (MedDRA) dictionary (the most up to date version that is available at the time of database build will be used and will be listed in the Data Management Plan (DMP)). The MedDRA dictionary will not be updated during the course of the study.

All AEs, including those which occurred prior to the first dose of IMP, will be listed. Only treatment emergent adverse events (TEAEs), i.e., existing conditions that worsen or events that occur during the course of the study after administration of IMP, will be included within the summary tables.

An overall summary of AEs will be produced including the number of TEAEs; the number and % of participants reporting at least 1 TEAE, serious TEAE, TEAE leading to withdrawal from the study; the number and % of participants reporting TEAEs by severity and relationship to IMP.

The number of TEAEs and the number and % of participants reporting at least 1 TEAE will be tabulated by system organ class (SOC) and preferred term. A participant reporting multiple episodes of a particular AE within a treatment period will only contribute 1 count towards the corresponding SOC and preferred term.

The number of TEAEs and the number and % of participants reporting at least 1 TEAE will be tabulated by preferred term and sorted by descending frequency on the total number of participants with that AE. A participant reporting multiple episodes of a particular AE within a treatment period will only contribute 1 count towards the corresponding preferred term.

In addition, the number and % of participants reporting TEAEs will be tabulated by maximum severity and strongest relationship to IMP. For the summary of TEAEs by severity, if a participant has multiple events occurring within the same SOC or preferred term the event with the highest severity will be counted. Similarly, for TEAEs by relationship to IMP, if a participant has multiple events occurring within the same SOC or preferred term, the event with the highest association to IMP will be counted.

Laboratory Safety: Biochemistry, haematology, coagulation, and urinalysis parameters will be listed with any out of normal range values flagged. Laboratory test results which are out of normal range will also be presented separately along with normal reference ranges. Descriptive

statistics (N, n, mean, SD, minimum, median, and maximum) of absolute and change from baseline (Day 1, pre-dose) values at each protocol-defined time point will be tabulated.

Vital Signs: Vital signs parameters will be listed with any out of normal range values flagged. Descriptive statistics (N, n, mean, SD, minimum, median, and maximum) of absolute and change from baseline (Day 1, pre-dose) values at each time point will be tabulated.

12-Lead ECG: 12-Lead ECG parameters will be listed with any out of normal range values flagged. Descriptive statistics (N, n, mean, SD, minimum, median, and maximum) of absolute and change from baseline (Day 1, pre-dose) values at each time point will be tabulated.

Additionally, the frequency (number and % of participants) for absolute and change from baseline QTcF values will be summarised according to the below categories:

For absolute values

- $QTcF \leq 450$ msec
- $450 < QTcF \leq 480$ msec
- $480 < QTcF \leq 500$ msec
- $QTcF > 500$ msec.

For change from baseline

- Decrease/no change
- $QTcF$ increase ≤ 30 msec
- $30 < QTcF$ increase ≤ 60 msec
- $QTcF$ increase > 60 msec.

10.11.8 PK Data

Concentration-Time Data: Individual plasma and urine AX-158 concentration-time data will be listed. Plasma and urine concentration-time data will also be summarised. The descriptive statistics presented will be N, n, arithmetic mean, geometric mean, SD, coefficient of variation (CV%), minimum, median, and maximum. Individual and mean plasma concentration-time data will also be plotted on both linear and semi-logarithmic scales.

For the purposes of summarising and plotting concentration-time data, concentration value(s) below the LLOQ will be assigned a value of zero if the timepoint is prior to treatment and LLOQ/2 otherwise.

Derived PK Data: The following PK parameters will be derived from plasma and urine AX-158 concentration-time data following administration of IMP using Phoenix WinNonlin (the most up to date version will be used and this will be documented in the SAP). Additional parameters may be reported as appropriate.

For the purposes of calculating PK parameters, concentration value(s) below the LLOQ will be assigned a value of missing.

Plasma:

- C_{\max} Maximum concentration.
- T_{\max} The time to maximum observed concentration.
- T_{lag} The delay in achieving T_{\max}
- λ_z Elimination rate constant.
- $t_{1/2}$ Terminal elimination half-life.
- AUC_{0-24} Area under the concentration-time curve (AUC) from 0 to 24 h post-dose.
- $AUC_{0-\tau}$ Area under the concentration-time curve (AUC) from 0 to τ , where τ is the dosing interval (planned, 0 - 24 h) (Part C only).
- AUC_{0-t} Area under the concentration-time curve (AUC) from the time of dosing to the time of the last measurable concentration.
- $AUC_{0-\infty}$ AUC extrapolated to infinity.
- $AUC\%$ extrapolated Residual area.
- CL/F Total apparent clearance following extravascular administration.
- V_z/F Apparent volume of distribution following extravascular administration.

Urine

- A_e Amount and cumulative amount of dose excreted in urine over each collection interval.
- $A_e\%$ % and cumulative % of dose excreted in urine over each collection interval.
- CL_R Renal clearance.

Derived PK parameters will be listed along with the points used to calculate k_{el} (lower, upper, and number used) and coefficient of determination (R^2) adjusted. The derived PK parameters will also be summarised. The descriptive statistics presented will be N, n, arithmetic mean, geometric mean (with the exception of T_{\max}), SD, coefficient of variation (CV%), minimum, median, and maximum.

Part A (SAD): Dose Proportionality/Independence. Dose proportionality will be assessed by performing a regression analysis of the log-transformed C_{\max} , AUC_{0-t} and $AUC_{0-\infty}$ values versus the log-transformed dose using the power model with a fixed effect for log (dose). For each parameter, a point estimate and 95 % confidence interval (CI) will be calculated for the slope of the regression line.

Dose independence will be assessed for $t_{1/2}$ and CL/F by performing a regression analysis of the untransformed parameters versus dose with a fixed effect for dose. For each parameter, a

point estimate and corresponding 95 % CI will be calculated for the slope of the regression line.

Part B (Food Effect): Following logarithmic transformation, C_{max} , AUC_{0-t} and AUC_{0-inf} values will be subjected to an ANOVA including fixed effects for treatment and participant. Point estimates and 90% CI will be constructed for the contrasts between treatments using the residual mean square error obtained from the ANOVA. The point and interval estimates will be back-transformed to give estimates of the ratios of the geometric least squares means (LSmeans) and corresponding 90% CI. Estimated geometric means will also be presented for each treatment.

Part C (MAD)

Dose Proportionality/Independence: For Day 1 and Final Dosing Day (Day 10), dose proportionality will be assessed by performing a regression analysis of the log-transformed C_{max} , AUC_{0-t} and AUC_{0-inf} (Day 1 only) values versus the log-transformed dose using the power model with a fixed effect for log (dose). For each parameter, a point estimate and 95 % CI will be calculated for the slope of the regression line.

For Final Dosing Day (Day 10), dose independence will be assessed for $t_{1/2}$ and CL/F by performing a regression analysis of the untransformed parameters versus dose with a fixed effect for dose. For each parameter, a point estimate and corresponding 95 % CI will be calculated for the slope of the regression line.

Steady-State: For each dose level, log-transformed trough concentration levels at pre-dose day 5 will be subjected to a mixed effects ANOVA with study day as a fixed effect and participant as a random effect in order to establish whether and when steady-state has been attained for each dose level. Back-transformed ratios for the comparisons of each consecutive day (i.e., Day 3/Day 2) will be presented along with corresponding 90 % CI.

Accumulation: For each dose level, log-transformed C_{max} and AUC_{0-t} values on Day 1 and Final Dosing Day (Day 10) will be subjected to an ANOVA with study day as a fixed effect and participant as a random effect. For comparison, point estimates and 90 % CI for the difference between Final Dosing (Day10) and Day 1 will be constructed using the residual mean square error obtained from the ANOVA for each dose level. The point and interval estimates will then be back transformed to give estimates of the ratios of the geometric least squares means and corresponding 90 % CI.

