11.4 PK ANALYSES

11.4.1 Concentration Data

Plasma PK samples will be collected for the measurement of AX-158 at the following time points:

Part A:

- Day 1 pre-dose, 30 mins, 45 mins, 1h, 2h, 3h, 4h, 6h, 8h, 12h
- Day 2: 24h, 36h
- Day 3: 48h
- Day 4: 72h

Part B: For both treatment periods

- Day 1 pre-dose, 30 mins, 45 mins, 1h, 2h, 3h, 4h, 6h, 8h, 12h
- Day 2: 24h, 36h
- Day 3: 48h
- Day 4: 72h

Part C:

- Day 1 and Day 10 pre-dose, 1h, 2h, 3h, 4h, 5h, 6h, 8h, 12h
- Day 2 and Day 11: 24h, 36h
- Day 3 and Day 12: 48h
- Day 4 and Day 13: 72h
- Day 5: pre-dose
- Day 6: Pre-dose
- Day 7: Pre-dose
- Day 8: Pre-dose

Plasma AX-158 concentrations will be listed along with blood sampling times and details of any sampling time deviations and summarised for each treatment using the descriptive statistics N, n, arithmetic mean,

geometric mean, arithmetic standard deviation (SD), coefficient of variation (CV%), minimum, median and maximum.

The individual subject plasma AX-158 concentration profiles over time will be presented graphically on both linear and semi-logarithmic scales with each subject on a separate plot. For Part C, Day 1 and Final Dosing Day (Day 10) profiles will be presented on the same plot. The geometric mean plasma AX-158 concentration profiles over time will be presented graphically on both linear and semi-logarithmic scales with all treatments on the same plot, with separate plots for Day 1 and Final Dosing Day profiles for Part C.

Urine PK samples will be collected for the measurement of AX-158 at the following time intervals: pre-dose and in intervals of 0-12, 12-24, 24-48 and 48-72 h post-dose on Day 1 and Day 10.

Urine AX-158 concentrations will be listed along with urine volumes and summarised for each treatment using the descriptive statistics N, n, arithmetic mean, geometric mean, arithmetic standard deviation (SD), coefficient of variation (CV%), minimum, median and maximum.

For inclusion within the summary tables and plots, plasma and urine concentrations below the lower limit of quantification (LLOQ) will be imputed as zero at pre-dose and as LLOQ/2 for post-dose samples. They will be listed as recorded. Data reported as not reportable or no sample/result will be handled as missing (i.e. no assumption will be made about the actual concentration).

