11.4.2 Derived PK Parameters

The derived pharmacokinetic parameters of plasma AX-158 will be determined from the individual concentration versus time data using WinNonlin Phoenix v8.3 or higher. The actual time of blood sample will be used in the calculation of the derived PK parameters. Should the actual time be unavailable but a blood sample was taken, the nominal time point will be assigned.

For the purpose of calculating PK parameters, BLQ values will be imputed as zero at pre-dose and set to missing for post-dose time points. If a Day 1, pre-dose result is missing, it will be imputed as zero. The following plasma AX-158 PK parameters will be calculated using standard non-compartmental methods:

Version:	3.0
Document Title:	SAP Template - Phase 1
Document Number:	TEMP-00109
Previous Document Number:	STATt008

Part A:

Pharmacokinetic Parameter and Unit	Definition	Computation	WinNonlin Parameter Name
C_{max} ($\mu\text{g/mL}$)	Maximum concentration.	Maximum observed concentration, occurring at T_{max} . If not unique, then the first maximum is used.	Cmax
T_{max} (h)	The time to maximum observed concentration.	Time of maximum observed concentration. If the maximum observed concentration is not unique, then the first maximum is used.	Tmax
λ_z (1/h)	Elimination rate constant.	First order rate constant associated with the terminal (log-linear) portion of the curve. Estimated by linear regression of time vs. log concentration; the regression analysis should contain data from at least 3 different time points in the terminal phase	lambda_z
$t_{1/2}$ (h)	Terminal elimination half-life.	$= \ln(2) / \lambda_z$	HL_Lambda_z
AUC_{0-24} ($\text{h}^*\mu\text{g/mL}$)	Area under the concentration-time curve (AUC) from the time of dosing to 24 h post-dose	AUC measured from the concentration at time of dosing to 24 hours post dose. The AUC is computed using the linear up-log down trapezoidal rule.	AUC0-24
AUC_{0-t} ($\text{h}^*\mu\text{g/mL}$)	Area under the concentration-time curve (AUC) from the time of dosing to the time of the last measurable concentration.	AUC measured from the concentration at time of dosing to the last measurable positive concentration. The AUC is computed using the linear up-log down trapezoidal rule.	AUClast
$AUC_{0-\infty}$ ($\text{h}^*\mu\text{g/mL}$)	AUC extrapolated to infinity.	AUC measured from the concentration at time of dosing extrapolated to infinity based on the last observed concentration.	AUCINF_obs

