Pharmacokinetic Parameter and Unit	Definition	Computation	WinNonlin Parameter Name
Ae (µg)	Cumulative amount of study drug excreted in urine during a time interval.	The sum of the individual urine volume * urine concentration of study drug. $= \Sigma (\text{Concentration} \cdot \text{Volume})$	N/A (calculated using SAS)
Ae% (%)	Percentage of study drug excreted in urine during a time interval.	$= 100 \cdot Ae / \text{Dose}$	N/A (calculated using SAS)
CLR (L/h)	Renal clearance.	$= Ae / AUC_{0-t}$	N/A (calculated using SAS)

The derived urine pharmacokinetic parameters Ae, Ae%, CumAe, CumAe%, CLR will be determined from the individual urine concentration versus time data using SAS EG v8.3 or higher.

Derived PK parameters will be listed along with the points used to calculate λz (lower, upper, and number used) and coefficient of determination (R^2) adjusted. The derived PK parameters will also be summarised. The descriptive statistics presented will be N, n, arithmetic mean, geometric mean (with the exception of T_{\max}), SD, coefficient of variation (CV%), minimum, median, and maximum.

Any $AUC_{\% \text{ extrap}}$ values greater than 20% will be flagged within the data listing. In accordance with regulatory guidance, the associated data should not be excluded from analysis but if this is observed for >20% of the profiles, the validity of the study may be in question.

In the instance of a significant sample time deviation ($\geq 5\%$ of nominal time i.e. 72 min) for the 24 h PK sample, the AUC_{0-24} values will be excluded from statistical analysis, but will be calculated, included in the derived PK data listing and flagged. Where a non-significant sample time deviation (≤ 72 min) for the 24 h PK sample occurs and the terminal elimination rate constant (λz) is estimable, this will be used to estimate AUC_{0-24} . Where a non-significant sample time deviation (≤ 72 min) for the 24 h PK sample occurs and the terminal elimination rate constant (λz) is not estimable, WNL is unable to estimate AUC_{0-24} . Therefore, in order for an AUC_{0-24} value to be estimated, the actual sampling time (including bleed time deviations) at the 24 h nominal time point will be used for the partial AUC settings.

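### The BLQ-to-missing rule reaches the urine parameters, where a BLQ interval is a known near-zero amount; the SAP should give urine its own rule (minor).

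*Protocol*

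**What the plan says.** Protocol 10.11.8 opens its derived-parameter text with "The following PK parameters will be derived from plasma and urine AX-158 concentration-time data following administration of IMP using Phoenix WinNonlin". The BLQ sentence follows: "For the purposes of calculating PK parameters, concentration value(s) below the LLOQ will be assigned a value of missing". The section then lists the plasma parameters and the urine parameters Ae, Ae% and CLR. Neither matrix is excepted. The other BLQ rule in that section ("concentration value(s) below the LLOQ will be assigned a value of zero if the timepoint is prior to treatment and LLOQ/2 otherwise") is for summarising and plotting concentrations only.

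SAP 11.4.2 states "For the purpose of calculating PK parameters, BLQ values will be imputed as zero at pre-dose and set to missing for post-dose time points". This sentence stands in the paragraph on plasma parameters. The urine parameters come later in the section, are calculated in SAS rather than WinNonlin, and have no BLQ rule of their own. Ae is defined as "The sum of the individual urine volume * urine concentration of study drug", Ae% as 100 x Ae/Dose and CLR as Ae/AUC0-t.

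SAP 11.4.1 names urine in its zero and LLOQ/2 rule, but for summary tables and plots only. The same paragraph adds: "Data reported as not reportable or no sample/result will be handled as missing". SAP 10.4 deals with missing blood samples and says nothing about a missing urine interval. SAP 1.2, which lists the changes from the protocol, does not mention BLQ handling.

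**The concern.** Setting a post-dose BLQ value to missing is tolerable for a plasma AUC, which is built by joining neighbouring samples. Ae has no such interpolation: each interval contributes its own concentration x volume. When the volume is recorded and the concentration is BLQ, the amount is known to lie between zero and LLOQ x volume. Coding it as missing discards that information.

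Two things follow. First, the interval's own Ae and Ae% drop out of the summary, so the interval mean describes only participants with quantifiable urine. Second, the cumulative values depend on how the SAS sum treats a missing term, and neither document says. SAP 12 relies on independent programming for quality control, so two programmers could both follow the plan and obtain different cumulative Ae, Ae% and CLR.

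**Working it through.** The plan states no figure on this point, so there is nothing to reproduce. The documents give no LLOQ, urine volume or urine concentration; the example below is assumed.

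**Inputs from the documents**
- Four post-dose intervals (0-12, 12-24, 24-48, 48-72 h) on Day 1 and Day 10 (Protocol Table 10.9.3, footnote 12).
- Six active participants per Part C cohort (SAP 3.3).
- Projected AUC of 1.17 µg·h/mL at 15 mg (Protocol Table 10.8.2).

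**Assumed inputs**
- Dose 15 mg (15,000 µg).
- Volumes 900, 700, 1600 and 1600 mL.
- Concentrations 0.5, 0.2 and 0.05 µg/mL, then BLQ at 48-72 h.
- LLOQ between 0.001 and 0.02 µg/mL.

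**Step 1: what a BLQ interval holds.** At most LLOQ x volume: 0.001 x 1600 = 1.6 µg to 0.02 x 1600 = 32 µg. That is 0.01% to 0.21% of the dose.

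**Step 2: cumulative values with one BLQ interval.** The quantifiable terms are 450 + 140 + 80 = 670 µg, so the true total lies between 670 and 702 µg.
- Sum propagates missing: Ae 0-72 h, its Ae% and a CLR based on it are missing. The cumulative values to 48 h survive.
- Sum skips missing: Ae = 670 µg, Ae% = 100 x 670/15,000 = 4.47%, CLR = 670/1.17 = 573 mL/h = 0.573 L/h. This is what a zero rule would give.

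**Step 3: the skipping sum when a collection is lost.** With 48-72 h counted as zero, the full total is 670 µg.
- 0-12 h lost: 670 - 450 = 220 µg (-67%), CLR 0.188 L/h.
- 12-24 h lost: 670 - 140 = 530 µg (-21%).
- 24-48 h lost: 670 - 80 = 590 µg (-12%).

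**Step 4: the interval summary.** This effect arises whichever way the sum works. Suppose k of 6 participants are BLQ in an interval and the others average m. The rule reports m. With BLQ as zero, the mean is (6 - k)m/6, so the reported mean is too high by a factor of up to 6/(6 - k): 1.2 for k = 1 and 2 for k = 3. If each BLQ interval really held the 32 µg maximum and m = 80 µg, the factors would be 80/[(5 x 80 + 32)/6] = 80/72 = 1.11 and 80/[(3 x 80 + 3 x 32)/6] = 80/56 = 1.43. In absolute terms, for k = 3, this is 80 µg reported against 40-56 µg: 0.53% of the dose against 0.27-0.37%.

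**Step 5: how easily a cohort is touched.** If each participant has probability p of a BLQ interval, the chance that at least one of six is affected is 1 - (1 - p)^6: 47%, 82% and 98% for assumed p of 10%, 25% and 50%.

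**The case against.** The strongest reply is that this is a gap in specification and not a rule that the SAP deliberately applies to urine. The SAP's BLQ sentence is in the plasma paragraph, and the SAP cites protocol version 5.0 while the protocol available is version 4.0, so the protocol sentence may since have changed. This stands in part. On the text available, however, the only rule that reaches Ae is the protocol's, SAP 1.2 does not withdraw it, and the alternative reading leaves urine with no rule at all.

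A reader might infer that BLQ and lost collections can no longer be told apart. The documents do not support this. SAP 11.4.1 lists BLQ values as recorded, Protocol 10.9.24 has the volume recorded after each interval, and the shell for Listing 16.2.5.8 shows collection times and urine weight. The two share a code only within the parameter calculation. SAP 11.4.1 also says that nothing is to be assumed about an absent result, which argues against counting it as zero, although that paragraph opens on tables and plots.

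It is also fair that a skipping sum already treats BLQ correctly in the cumulative total. The harm in that branch comes from a lost collection, which is a separate gap, and participants are resident throughout the urine intervals. Even when missing values propagate, other intervals and the earlier cumulative values remain. The summaries show n, so a reduced count would be visible, though not its cause.

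**Conclusion.** The concern holds as a minor point. As written, the protocol rule removes interval Ae and Ae% for a BLQ urine interval and so tends to bias interval summaries upward. Volumes that differ widely between participants could blur this. Whether cumulative Ae, Ae% and CLR are also lost depends on an unstated programming choice.

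The size cannot be fixed from the documents, and every amount above except the AUC projection rests on assumed values. A reader might go further and infer that cumulative excretion will be materially overstated because only high excreters keep complete totals. That would need many participants lost and BLQ status closely tied to total excretion. Late BLQ also depends on half-life and urine dilution, and the documents give no frequency.

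The impact is confined to the secondary urine parameters in Part C, which are summarised descriptively. The safety objective, the plasma PK and the escalation rule, which uses plasma Cmax and AUC0-24, are untouched.

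**What to change.** Limit the BLQ-to-missing rule to post-dose plasma and add to SAP 11.4.2, for urine:

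- A BLQ concentration with a recorded volume contributes zero to Ae for that interval.
- A lost, incomplete or unreportable collection leaves that interval missing and flagged, together with all later cumulative Ae and Ae% and any CLR built on them.
- How zero interval amounts enter the geometric mean that the SAP requires for derived parameters. The small offset in SAP 11.4.1 is defined for pre-dose concentrations only. One option is to report the number of BLQ intervals beside a geometric mean of the positive values, labelled as such.

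Record the change in SAP 1.2. Using LLOQ/2 x volume instead of zero is also defensible: the example total becomes 670.8-686 µg, and zeros no longer arise. After a late lost collection, CLR could alternatively be computed with Ae and AUC matched over the completed intervals, if that is stated in advance.

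The cost is a few SAP sentences before database lock and a small SAS change. The price of the zero rule is an underestimate of Ae by at most LLOQ x volume for each BLQ interval.
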